Fingerstick and serum HbA1c and Fructoasmine: The HbA1c test is a blood test that provides information about a person's average levels of blood glucose over the last 3 months. Fructoasmine is a blood test that provides information about the average blood glucose over 2 weeks. The DCA Vantage Analyzer HbA1c assay tests for a quantitative determination of HbA1c in human whole blood, and provides immediate test results from a finger prick of blood. Serum HbA1c and fructoasmine is sent via LabCorp.

CBC: The complete blood count (CBC) is a test that evaluate the cells that circulate in blood, including red blood cells (RBCs), white blood cells (WBCs), and platelets (PLTs). CBC will be conducted at baseline and week 34-36.

M: Questionnaires

Nutrition Questionnaire (Appendix G): Starting The Conversation (STC) is an eight-item simplified food frequency instrument designed and validated for use in primary care and health-promotion settings (12).

Physical Activity Questionnaire (Appendix H): The International Physical Activity Questionnaire (short) is a validated questionnaire that reviews the last 7 days of activity for middle aged adults (age 15-69 years) (13).

Diabetes Distress Questionnaire (Appendix O): Problem Areas in Diabetes Scale 5 (PAID-5), is a 5-item validated short form of the PAID-20. The PAID has been used in women with GDM. The questionnaire consists of 5 items, scored on a 5-point Likert scale ranging from 0 (not a problem) to 4 (a serious problem). Total scores can range from 0 to 20, with higher scores suggesting greater diabetes related distress. A cutoff of 8 or higher indicates elevated diabetes distress (14-15).

WHO-5 well-being index (appendix I) is a marker of overall welling and has been used to evaluate overall health in type 1 and type 2 diabetes (21)

Depressive Symptoms Questionnaire (Appendix P): The Patient Health Questionnaire 9 (PHQ-9) will be used. The PHQ-9 score ranges from 0 to 27: each of the 9 items is scored from 0 (not at all) to 3 (nearly every day), in which higher scores indicate more depressive symptoms Research has shown that a cutoff of 12 or higher is suitable to identify elevated depressive symptoms in patients with diabetes (15-18).

Perception/Satisfaction with CGM and Fingersticks/Meter (Appendices J): The Harvard Joslin Diabetes Center has developed a series of questionnaires on CGM experiences, opinions and expectations that will be given at the end of the intervention and has been adapted for the GDM. Additionally, questions about food changes and activity changes that was created for CGM use(19,20) . Questionnaires have been adapted for use in those using only meter fingersticks and for GDM.

Sleep Questionnaire (appendix Q) The Pittsburgh Sleep Questionnaire is good tool for screening sleep disorders in the population and has been used in pregnancy (22,23)

N: Glucose/CGM Data /Evaluation Measures: The compliance and duration wear for participants with CGM will also be recorded. Glucose dynamics, e.g., average glucose, standard deviation, mean amplitude of glucose excursion (MAGE), time in range % (65 and 140 mg/dL), % high (>140 mg/dL), % low (<64 mg/dL), and severe low % (<54mg/dL) and coefficient of variation (CV) and other statistical measures of glucose variability in those with CGM will be reviewed from the RT- CGM device data at baseline and visit 2-4. Blinded CGM values will be obtained at baseline and visit 2 and 3.

Glucose meter: Compliance with fingersticks 4 times a day will be recorded by average number of fingersticks per day. Glucose data including: average glucose, standard deviation, mean amplitude of glucose excursion (MAGE), time in range % (65 and 140 mg/dL), % high (>140 mg/dL), % low (<64mg/dL), and severe low % (<54mg/dL) will also be recorded.

N:Antenatal Ultrasound Markers: estimated fetal weight (in grams and percentile) using Hadlock scale, Biparietal Diameter, Head circumference, abdominal circumference, and femur length. Amniotic Fluid Index.

O: Delivery Outcomes:

Obstetric Outcomes:

- 1.Gestational age at delivery
- 2.Labor status (spontaneous labor, induced labor, no labor). For induced labor include indication for induction
- 3.Mode of delivery (vaginal delivery, cesarean delivery, operative vaginal delivery) including indication for delivery
- 4.Shoulder dystocia: defined as a delivery that requires additional obstetric maneuvers to release the shoulders after gentle downward traction has failed. SD occurs when either the anterior or, less commonly, the posterior fetal shoulder impacts on the maternal symphysis or sacral promontory

Maternal Outcome:

1. Preeclampsia or GHTN
2. Maternal insulin or medication use
3. Maternal hypoglycemia: symptoms or asymptomatic biochemical hypoglycemia (fingerstick or RT-CGM less than 54 mg/dL (3.0 mmol/L), severe (fingerstick or RT-CGM < 64mg/dl (3.6 mmol/l)
4. Maternal weight gain

Fetal Outcome:

1. Gestational age at delivery
2. Live born or stillbirth

3. Birth weight: (large for gestational age, small for gestational age, macrosomia, birthweight ratio). Large for gestational age: birthweight > 90th centile for gestation using Fenton 2013 growth charts. Small for gestational age: birthweight below the 10th centile using Fenton 2013 growth charts. Macrosomia: birthweight ≥ 4 kg.
4. Birthweight ratio (birthweight adjusted for gestation and gender calculated with the Fenton 2013 web calculator (<http://peditools.org/fenton2013>)).
5. 5- minute Apgar score
6. Respiratory distress
7. Neonatal hypoglycemia: defined as < 4 h of life: < 1.4 mmol/l (30 min after first feed); < 2.2 mmol/l (1 h after subsequent feeds), 4–24 h of life: < 1.9 mmol/l (prefeed); < 2.5 mmol/l (1 h after feed)
8. NICU admission including LOS
9. Birth injury (such as brachial plexus injury)
10. Hypoxic ischemic encephalopathy

P. Risks and Side Effects:

There are various possible risks and side effects that a participant may incur as a result of this study. At the beginning of the study, when participants are administered the informed consent form by research staff, they will be informed that their participation is completely voluntary and will be informed of the risks and benefits. They are free to leave the study at any time and will not be penalized. Potential subjects will also be told that failure to participate in no way affects the usual care they would receive from their OB provider. Only after all questions have been answered, both study staff and the participant will sign and date the consent form.

It is very unlikely that there will be any adverse events

There are possible risks associated with the intervention activities, including the medical device, including:

- a. Less Likely (1% \leq Event Rate < 5%): CGM site infection or tape allergy (<1-2%) (41)
- b. Likely (5% \leq Event Rate < 10%): None
- c. More likely (Event Rate $\geq 10\%$): None

Risk to Participants:

There is the possibility of bruising, soreness and infection at the sites of needle sticks for blood draws, finger sticks for checking glucose levels and at the insertion sites of the CGM device. All participants will be provided with an emergency number for who to contact if any problems arise.

Continuous Glucose Monitoring Device: Participants may have temporary discomfort at the time of inserting the small filament. This can include bruising or redness of the skin, rare allergy to tape used to keep the device in place, infection at the insertion site, and potential perceived dislike of having a medical device on them for 10 days.

There is the risk of lightheadedness, dizziness and fainting from having blood drawn.

There is the possibility of potential embarrassment answering questionnaires. Participants are told they can leave questions blank if they are uncomfortable answering them.

There is the risk of anxiety because the medical history contains some sensitive questions like alcohol and drug history and questions about previous pregnancies.

There may be confusion about when to test blood sugar which could cause anxiety. Participants will be told to follow the instructions of their provider. Participants will be provided with study contacts for any questions and the study will work in conjunction with the participants' OB provider about blood sugar testing instructions.

There is the risk for participants in RT-CGM in the intervention group missing alerts if the alert notification is turned off.

There is the risk of lack of accuracy of the CGM read outs in the intervention group if the participant takes acetaminophen.

There is the risk for both groups if during insertion of the CGM the insertion wire breaks and becomes lodged under the skin and requires removal.

There are some skin issues that can occur when using the CGM device such as allergic reactions to the device that are localized and can include bruising, rash, soreness, and infection. This skin reaction can also be caused by the tape used to secure the device.

There is the risk of suicidal ideation presenting itself while answer the PHQ-9 questionnaire. If the subject endorses suicidal ideation answering the PHQ-9 our plan will be to call the participant immediately and discuss the participant's answer, provide the participant the number for a suicide hotline, and to call the PI if the participant endorses the intent to hurt themselves. The PI of the study will be notified immediately and will make the decision to call 911.

We will be checking for completion of the questionnaires after links to participants are sent to them and the PHQ-9 answers will be checked at that time. Our time frame for checking the PHQ-9's completion is within 3-5 days after being sent out. Our plan will be put into action if any questions are answered in a manner concerning to our study personnel who will be trained for our action plan and what to watch for within an hour of seeing the answer to the question

Body measurements: Participants may experience discomfort or embarrassment associated with weight and fundus measurements.

Q. Benefits:

Participants may receive some benefit for glucose control in pregnancy with RT-CGM which may or may not translate to improved fetal and maternal outcomes. Control patients will likely receive no benefit from blinded CGM and fingersticks 4 times a day fasting and post-meals as these are the current standard of care in GDM. This research may benefit society by enhancing our understanding of medical devices use in GDM and thus help establish new procedures and practices that are associated with GDM.

R. Conflicts Of Interest:

No conflicts of interest are noted.

S. Confidentiality:

All of the subjects' personal information, clinical data and consent documents will be stored in a secure location in a locked file cabinet in the University of Washington OB research coordinator's office. The subjects' personal information and research related clinical data other than routine laboratory results will be accessible only to the Principal Investigator and the research staff associated with the study. Organizations that may

inspect and copy the participant information include the IRB of the University of Washington. A master code linking the unique study numbers with subjects' identifying information will be kept by the Principal Investigator or by the Project Officer in a locked file cabinet. Additionally, all data collected by coordinators will be entered and managed through the encrypted Research Electronic Data Capture (REDCap) system maintained at University of Washington. All data is de-identified with no personal health information entered (PHI). REDCap was developed specifically around HIPAA security guidelines. REDCap has been disseminated for local use at more than 940 other academic/non-profit consortium partners in 75 countries. REDCap servers are housed in a local data center at CNMC, and all web-based information transmission is encrypted. This system is accessed through a secure login and password. Only the RedCap database coordinators and study staff will have access privileges to the University of Washington data set and will be strictly prohibited from sharing passwords. All will undergo the standardized authorized training provided by the REDCap team. Staff will maintain files in password-protected documents on HIPAA-compliant servers. REDCap programmers build in quality controls for the data that will be collected according to their stringent protocols. Data will be stored for 3 years after study completion for possible re-analysis and sub-group analysis that the clinical team may determine to be useful. More information about the consortium and system security can be found at <http://www.projectredcap.org>. [name] and her research team will destroy the informed consent, research source documents, data files, and master code 3 years after the completion of the study. This will allow time for the PI and collaborators to reexamine the data as needed in the revision process for manuscripts submitted to peer-reviewed journals.

All information that the study subjects provide study personnel is for research purposes only and, as such, names and any other identifying information will not be reported or published in papers, presentations, or proposals that result from this research.

When the subject enrolls in the study, she will be assigned a unique study number that is not any part of her social security number or other personal identifier. These unique study numbers will be used to identify all information that subjects provide and any information that is collected from their medical records. The unique study numbers will be assigned sequentially according to the order of study enrollment and subjects will be identified by the initials of the group to which they are randomized and 3 numbers according to their entry into the study beginning with 001. Therefore, the first subject randomized to the DMC (control) group will be DMC-001 and the first subject randomized to the DMCGM (intervention) group will be DMCGM-001. A total of 50 DMC and 50 DMCGM subjects will be enrolled.

Although every precaution is being taken to protect participant privacy, breach of confidentiality is always possible. In the unlikely event of a breach of confidentiality, the nature of the research data is not of a sufficiently personal nature to negatively affect employment status, lead to civil/criminal liability, incur financial risks to the study participants, or other risks.

T. Subject Compensation:

Participants will be given \$50 after visit 0 and \$50 after visit 3. Visit 3 compensation will be given to participant upon return of blinded device or RT-CGM download at 34-36 weeks. If lack of CGM data necessitates unscheduled visits, the participant will receive an additional \$25 per visit up to a maximum of \$50 if 2 unscheduled visits are required. Subjects will also have use of the medical devices during the study for free: in the intervention group they will receive a glucose meter and test strips (total 50 test strips for free) to be used as needed. In the control group they will receive a glucose meter and 400 test strips for free if not covered by their insurance. No additional cost will be incurred by subjects.

If extra visits are necessary we will follow the OB clinic guidelines for COVID 19 screening. This money can be used for travel and parking but all study visits are piggy backed to a regular clinic visit so no extra travel or parking is required by the study although visits may be a little longer than usual

U. Appendix:

- A. Educational Material: Real-Time Continuous Glucose Monitoring educational material (A1) or Fingerstick educational material (A2)
- B. Table of Study Measurements
- C. Pre-Screening Checklist Telephone

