Oct 18 2024

Clinicaltrials: Study 00011755

INVESTIGATOR-SPONSORED STUDY

The Use of Real-Time Continuous Glucose Monitoring (RT-CGM) in Gestational Diabetes

[name], [name], [name].

Division of Metabolism, Endocrinology and Nutrition

**Department of Medicine
University of Washington
[name]
[name]
[name]**

Correspondence to:

**[name]
Assistant Professor
Email: [contact]
[contact]**

Table of Contents

A. Specific Aims/ Hypothesis.....	4
B. Background.....	4
C. Significance:	4
D. Research Recruitment and Population.....	5
E. Statistical Considerations.....	6
F. Inclusion/Exclusion Criteria.....	7
G. Diagnosis of GDM.....	8
H. Study Design.....	9
I. Randomization.....	12
J. Study Procedures, Materials and Devices.....	13
K. Measurements.....	14
L. Collection of Human Biological Specimens.....	15
M. Questionnaires.....	16
N. Glucose/CGM Data /Evaluation Measures.....	17
O. Antenatal Ultrasound Markers.....	17

P. Risks and Side-Effects.....	17
Q. Benefits.....	18
R. Conflict of Interest.....	18
S. Confidentiality.....	18
T. Compensation.....	19
U. Appendixes.....	19

RESEARCH PROTOCOL

TITLE: A Study on the Use of Real-Time Continuous Glucose Monitoring (RT-CGM) in Gestational Diabetes

A. Specific Aims/ Hypothesis: We hypothesize that use RT-CGM in those with gestational diabetes will improve/ reduce glycemic variability in pregnancy and potentially improve fetal and maternal outcomes.

Aim 1. Evaluate if Real Time Continuous Glucose Monitoring improves mean glucose, time in range, time above and below range, mean amplitude of glycemic excursions (MAGES) and standard deviation of blood sugars and coefficient of variation (CV)

Aim 2. Evaluate if improved glycemic variability improves fetal and maternal outcomes in pregnancies affected by gestational diabetes.

Aim 3: Evaluate participants' perception of RT-CGM use in pregnancies affected by gestational diabetes.

Aim 4: Evaluate nutritional and lifestyle changes in GDM and pregnancy and effect of RT-CGM

Aim 5: Evaluate if RT-CGM decreases need for initiation of oral diabetes medication and/or insulin. If insulin initiated, evaluate if RT-CGM reduces cumulative insulin dose.

Aim 6: Evaluate nocturnal hypoglycemia in pregnancy and if RT- CGM lessens nocturnal hypoglycemia

B. Background and Significance

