A maximum number of 130 participants will be recruited that meet inclusion/exclusion criteria for the study. Dropouts will be replaced on a one-to-one basis as needed to reach a total of 95 completed/evaluable participants. Recruitment information about the study will be made available to all obstetrics and gynecological medical personnel including medical assistants, nursing staff, and physician and physician extenders at the University of Washington and associated obstetric sites by medical staff announcements and provider flier (Appendix F). Information about the study will be made available to patients by a study flier (Appendix H) which will provide contact information for the study coordinator. If potential participants express interest in the study to medical staff, permission for the study coordinator to contact them via telephone or email will be requested and potential participants will be contacted for further screening and potential enrollment. A HIPAA Partial Waiver of Research Subject Authorization Request (HRP-281) will be requested if needed so that the study coordinator(s) can pre-screen provider's clinics and approach potential eligible subjects at the time of their visit. This may also be used to complete a database search to identify potential eligible subjects ahead of a clinic visit that have elevated A1c or positive oral glucose tolerance test.

Subjects may also be identified through posters and flyers placed in the community, as well as through all University of Washington clinics and in the broader community through websites and other advertisements. Potential subjects who satisfy the study criteria and express interest in the study will be given information about participation either by mail, email or a phone call. Eligibility questions will be asked but no study related procedure will be performed until informed consent/authorization has been obtained (see Appendix C).

Please note that pre-screening questions are done prior to consent then once the participant has signed consents further screening will be completed.

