Week 2 (Visit 1a): Gestational Age 14-16 (Early GDM Dx) or 24-28 weeks (Regular GDM Dx)

RT-CGM and meter will be downloaded for intervention group and meter downloaded for the control group. Glucose logs will be collected. All participants will confirm they have completed RN gestational DM education and nutrition appointments per local standard of care. Vital signs, weight and medications and dose will be recorded at each visit and maternal ultrasound results if available (appendix M).

Week 6 (Visit 1b): Gestational Age 20-22 weeks (Early GDM Dx)

RT-CGM and meter will be downloaded for the intervention group and meter downloaded for the control group. Vital signs, weight and medications and dose will be recorded at each visit and maternal ultrasound results if available (appendix M).

Week 6/Week 14 (Visit 2): Gestational Age 30-32 weeks (Both Early GDM Dx and Regular GDM Dx)

RT-CGM and meter will be downloaded for the intervention group and meter downloaded for the control group. Vital signs, weight and medications and dose will be recorded at each visit and maternal ultrasound results if available (appendix M).

The control group will wear blinded CGM for 10 days and return during regularly scheduled OB visit. The study staff will follow up with participants to remind them to return the devices. If for any reason, the CGM device fails to capture at least 3 days of data, the participants may be asked to repeat this measurement at an unscheduled visit.

Week 10/Week 18 (Visit 3): Gestational Age 34-36 weeks (Both Early GDM Dx and Regular GDM Dx)

RT-CGM and meter will be downloaded for the intervention group and meter downloaded for the control group. Vital signs, weight and medications and dose will be recorded at each visit and maternal ultrasound results if available (appendix M).

Questionnaire on nutrition and exercise in pregnancy and satisfaction with CGM and lifestyle changes with CGM.

The control group will wear blinded CGM for 10 days and return during regularly scheduled OB visit. HgA1c and fructosamine will be collected.

The study staff will follow up with participants to remind them to return the devices. If for any reason, the CGM device fails to capture at least 3 days of data, the participants may be asked to repeat this measurement at an unscheduled visit.

Week 14 /Week 22 (Visit 4) Gestational Age 38- 40 weeks (Both Early GDM Dx and Regular GDM Dx)

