- Participants with applicable smart phones may have CLARITY® push notifications on the CLARITY® mobile app about weekly time in range comparison enabled during the study.

- For app users, the “Share and Follow” functionality will be discussed and encouraged (i.e. the study participants are able to invite followers to review their glucose levels).

- For participants using the receiver only, the receiver will be downloaded into the CLARITY® clinic account at each visit. CGM data and reports. RT CGM-Participants will also keep a logbook of their blood sugars for their provider to review.

Control Group

The participants of the control group will perform self-monitored blood glucose testing with a study-provided blood glucose meter, including testing supplies. They will perform capillary blood glucose monitoring as routinely used for patients with GDM, i.e., at least four capillary blood glucose values daily including measurements in a fasting state as well as 1h after starting each meal. The study participants will keep a logbook of their glucose values

Each participant of the control group will be assigned a study blood glucose meter to measure and store their blood glucose values during the study.. A commercially available desktop software used in conjunction with the glucose meter for blood glucose monitoring will be utilized for downloading the meter data at each visit ensuring that dates and times are correct. Blood glucose meters used by the control group will be assessed to establish frequency of testing (overall and per week) as well as percentage of days with less than four measurements per day.

Subjects who got randomized to the control group then decided to withdraw from the study and discontinue their participating in the study will receive an email asking them to fill out a survey questionnaire to explain the main reason and any other reasons for withdrawal from the study. The survey will be sent to subjects’ email through a link from Redcap and it won’t take more than 10 minutes to complete.

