Glucose Meter: A glucometer is a device for measuring the concentration of glucose in the blood by placing a small drop of blood on a disposable test strip where a chemical reaction with glucose alters the electrical conductivity of the strip. It records glucose and also records average glucose and standard deviation and goal range can be set and show time in range. This is standard of care for patients with gestational diabetes in pregnancy to check fasting and 1 or 2 hours post-meals.

Gestational DM Nutritional Classes:

As per local standard of care, nutritional counseling for GDM is provided to all patients with diagnosis of GDM and all participants will be offered and asked to complete this session. Completion of session will be assessed at visit 2.

RT-CGM Handout:

A simple educational handout has been developed to explain glucose goals in pregnancy and also how food and activity affects blood sugars. This handout will be reviewed with RT-CGM participants at visit 0 and adapted to fingersticks as well for the control group (see Appendix A1, A2)

K .Measurements (Appendix C): We will measure HbA1c and fructosamine at the beginning of the study period and HbA1C at 30-32 and HbA1C and fructoasmine at 34-36 weeks. At each visit, blood pressure, maternal resting heart rate, maternal weight and height will be measured. At baseline and 34-36 weeks,

questionnaires on diet and physical activity and personal wellness questionnaires will be obtained. In the intervention group at 34-36 weeks, a questionnaire about CGM technology and perception of benefit of CGM use will be obtained.

Anthropometrics: Height will be recorded in centimeters and inches by a stadiometer. Weight will be recorded in pounds and kilograms using a Digital scale. Two measurements will be taken, and the average will be used. **Blood pressure and pulse** are taken with an Professional Digital blood pressure machine. Two measurements will be obtained at each appointment. If performed via remote televisit then patients will use their own blood pressure cuff and available scale.

L. Collection of Human Biological Specimens:

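### In the available text the Aim 3 questionnaire on RT-CGM is scheduled only at 34–36 weeks, so intervention women who have left by then give no data and reported perception is likely, though not certain, to be too favourable

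*Combined protocol and SAP*

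**What the plan says.** All references are to the combined protocol and SAP.

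- Section A, Aim 3: the target is participants' "perception of RT-CGM use in pregnancies affected by gestational diabetes". It is not restricted to women who complete the study.
- Section K: "In the intervention group at 34-36 weeks, a questionnaire about CGM technology and perception of benefit of CGM use will be obtained".
- Section H, Visit 3 (34–36 weeks): "Questionnaire on nutrition and exercise in pregnancy and satisfaction with CGM and lifestyle changes with CGM". No other visit in Section H lists this questionnaire.
- Section M describes questionnaires on "CGM experiences, opinions and expectations that will be given at the end of the intervention".
- Section J has intervention women wear RT-CGM continuously until the pregnancy ends, and Section H has a further visit at 38–40 weeks.
- Section J, control group, gives the only withdrawal survey. It is for "Subjects who got randomized to the control group then decided to withdraw from the study", it asks for reasons for leaving, and it goes out as an emailed REDCap link.
- Section D: "Dropouts will be replaced on a one-to-one basis as needed to reach a total of 95 completed/evaluable participants".
- Section E plans a CONSORT diagram and a comparison of completers with non-completers on demographics and baseline health.
- Section N records CGM compliance and duration of wear.
- Section P lists insertion discomfort, skin reactions, infection and dislike of wearing the device among the risks.

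**The concern.** Perception is the outcome, and perception can also be a reason for leaving. A woman who leaves because of a skin reaction, or because she dislikes the device, is one whose view matters for Aim 3, and the plan has no step that collects it. What is reported would then describe women who were still present at 34–36 weeks, while Aim 3 speaks of participants in general.

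The wait before the question is asked is long. By the Section H timeline, a woman diagnosed early is screened at about 14 weeks, so 20 to 22 weeks pass before Visit 3. A typical-risk woman screened at 24–28 weeks waits about 6 to 12 weeks (34 − 28 to 36 − 24).

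At stake is how far the satisfaction and perceived-benefit results of this pilot can be read as the view of women assigned to RT-CGM. The HbA1c comparison is not affected.

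**Working it through.** **Is there any route by which an early leaver is asked?** The plan states no figure for Aim 3 that could be reproduced, so this step compares the sections.

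- Sections H and K agree on one time point, 34–36 weeks.
- Section M's timing matches neither case. For a woman who completes, RT-CGM continues past Visit 3, so 34–36 weeks is not when her intervention ends. For a woman who stops early, her intervention ends before Visit 3, but no visit or contact is described that would deliver the questionnaire then.
- The Section J withdrawal survey covers the arm that does not use RT-CGM, and it asks about reasons for leaving.
- The Section E completer comparison uses baseline variables, and Section N records wear. Both describe who left and how long the device was worn. Neither measures perception.
- The Section E mixed models are specified for HbA1c, fructosamine, CGM readings and glycaemic variability. With a single perception measurement at Visit 3, a woman who left earlier has no Aim 3 value to enter in any model.

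**How large could the effect be?** Let d be the share lost before Visit 3, p_c the favourable share among completers and p_l the favourable share among leavers.

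- Favourable share in all women assigned = p_c(1 − d) + p_l·d.
- Overstatement = p_c − [p_c(1 − d) + p_l·d] = d(p_c − p_l).

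Inputs:

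- Section E needs 92 and enrols 100, so d = 1 − 92/100 = 8%. This is pooled over both arms. Using it here assumes that the RT-CGM arm loses the same share and that all of that loss comes before Visit 3.
- The gap p_c − p_l is not in the documents. The assumed range is 20, 40 or 60 points.

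Results at 8% loss:

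| Assumed gap | Overstatement |
|---|---|
| 0 points | 0 |
| 20 points | 0.08 × 20 = 1.6 points |
| 40 points | 0.08 × 40 = 3.2 points |
| 60 points | 0.08 × 60 = 4.8 points |

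As an example, suppose 90% of completers and 30% of leavers are favourable. Then the share in all assigned is 0.90 × 0.92 + 0.30 × 0.08 = 85.2%, against 90% reported, a difference of 4.8 points.

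**Comparison with sampling error.** With 46 respondents (92% of 50) and 80% or 90% favourable (assumption), the 95% half-width is 1.96 × √(0.8 × 0.2/46) = 11.6 points or 1.96 × √(0.9 × 0.1/46) = 8.7 points. The possible bias at planned attrition is smaller than this, but the interval does not account for it.

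**The case against.** The strongest reply is that the direction and size are inferred. The documents give neither a loss rate nor reasons for leaving in the RT-CGM arm. If leavers feel as completers do, the bias is zero. Women who deliver before 34–36 weeks are also missed, and their absence need not push the result upward. Section P puts site infection or tape allergy at no more than 1–2%. If 2% left for that reason with a 60-point gap (assumption), the shift would be 0.02 × 60 = 1.2 points. Dislike of the device would add to that, but no rate is given for it. A woman who stops wearing the sensor but still attends Visit 3 could be asked there. Aim 3 is descriptive, in a self-described pilot sized on HbA1c. All of this stands, and it limits how firmly the point can be put.

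Two stronger readings are tempting, and the documents do not support them.

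- A reader might take the recruitment ceiling as the expected loss: "A maximum number of 130 participants will be recruited" for 95 evaluable gives 1 − 95/130 = 26.9%, and a 20 to 60 point gap would then give about 5.4 to 16.2 points. But 130 is a maximum, replacement is only as needed, and the figure pools both arms. That the withdrawal survey was written for controls suggests, without proving, that control losses were the worry.
- A reader might infer that one-to-one replacement hides the loss. The CONSORT diagram and the completer comparison are there to make attrition visible. A replacement woman is herself randomised, so she need not enter the RT-CGM arm. Replacement adds no perception data on those who left, but it does not conceal that they left.

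It can also be said that Section M's timing could be read to include early stopping, and that Appendix B (the measurement table) and Appendix J (the questionnaire) are not in the text available. That is fair. The point is therefore confined to the available text, where no procedure carries out that reading.

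**Conclusion.** The gap holds on the available text: followed as written, the plan limits Aim 3 to intervention women still present at Visit 3, and Section M does not agree with Sections H and K on timing. That reported perception will be too favourable is likely, because Section P gives device-related reasons to leave, but it is not certain. At the planned 8% loss the illustration is 1.6 to 4.8 points. It rests on pooled attrition applied to one arm, all loss falling before Visit 3, and an assumed gap of 20 to 60 points. The 27% figure is a pooled ceiling and should not be used as an expected RT-CGM loss.

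The effect is modest at planned attrition. The change is still worth making, because without answers from early leavers the investigators could not show that the bias is small.

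**What to change.** - In Sections H, K and M, give the Appendix J CGM questionnaire at 34–36 weeks or, if earlier, when a woman stops RT-CGM, withdraws or delivers. Use the REDCap email link already in place for control withdrawals.
- Reconcile the timing in Section M with this, and check that Appendix B agrees.
- In Section E, state that Aim 3 is reported with the number responding out of all women randomised to RT-CGM. Show early-stop and 34–36-week answers separately and not only pooled, since they follow very different lengths of wear.

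The cost is one extra trigger for an existing questionnaire and a sentence or two of text. Treatment, sample size and the visit schedule do not change. Some early leavers will not respond, so the gap will narrow but not close. Their answers reflect shorter wear, and reported acceptability may come out slightly less favourable.
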